If the patient wishes to stop the antiepileptic drug, a trial of smaller doses of the same treatment will be offered. Upon refusal, or failure despite a reduction in doses, TPM will be offered to the patient if he had LEV and vice versa. This change of group will only be possible after 2 months from the beginning of treatment. These data will not be included in the calculation of the primary outcome, but can still be analyzed as a secondary outcome to assess whether changing patients from one group to another allows them to fully resolve the TNS. Patients who fail both treatments, or who refuse to attempt the treatment in the other group will be excluded from the remainder of the study and treatment with another antiepileptic recognized in the treatment of focal seizures as well as an usual follow-up will be offered.

Participant calendar

Table 4 – Participant calendar

Recruitment (Day 1)	Randomizatio n (After recruitment)	Phone follow-up (Week 2)	Clinic follow-up (Month 2)	Clinic follow-up (Month 4)	Phone follow-up (Month 6)
Standardized questionnaires : Epidemiological	Start of treatment	Medical assessment with	Medical assessment with	Medical assessment with	Medical assessment with
data Clinical features	EEG daily x 2 MRI if needed	standardized questionnaire	standardized questionnaire	standardized questionnaire	standardized questionnaire

Collection method

Sources: Data will be collected initially with the help of the patient's medical record. Subsequently, the rest will be completed entirely by the patient or his family. The evaluations will be guided by standardized questionnaires.

For patients with ECoG, continuous waveforms will be recorded for the entire period the electrode will be implanted, either up to the recording of 5 TNS episodes or up to 72 hours of recording.

The data will be collected double blind. The person administering the questionnaire and the person analyzing the data will not know the patient's group. In addition, a study number will be assigned to all patients during randomization and this is going to identify the patients on the questionnaires. Thus, the data will be entered into the Excel software anonymously. Following the study, the data will be kept for a period of 25 years, in a file locked with a password that will be in the research nurse's locked filing cabinet.

Data analysis

Statistics

Statistical analysis of the various data will be done with the help of the Statistical Package for the Social Sciences (SPSS) software. Most of the data will be analyzed by members of the research team. If necessary, the statistician of the CRC (Clinical Research Center) will be consulted.

The results will be analyzed by "intension-to-treat" given the expected dropouts in the two treatment groups.

Primary outcome: To assess the efficacy of TPM compared to LEV in the treatment of TNS in the context of SDH with negative EEG. To do this, it will be necessary to compare the rate of complete resolution of symptoms between the two groups. Our study comprising two independent groups and this variable being dichotomous (resolution: yes or no), a Chi-Square test will be used. This same test will also be used to compare the response of TPM in the NESIS versus non-NESIS subgroups and the same comparison with LEV will also

be performed. Subsequently, as sub-analyzes, the decrease in the frequency, intensity and duration of episodes (continuous variables) will also be compared in the two groups using a Student's T-test after validation of assumptions underlying the test.

Secondary outcome: tolerance to the antiepileptics used. To do this, we will analyze the comparison of the dropout rate (dichotomous variable: yes or no) and the side effect rate (categorical variable) using a chi-square test.

Degree of significance

We retained a significance level corresponding to an error α of 5%, whether a value p<0.05. The accepted beta error (β) is 10%, for a power of 90%.

Missing data

Patients with a large number of missing data or not including the data necessary to calculate the primary outcome will be excluded from the study. Those with some missing data that do not allow certain calculations of secondary outcomes will be kept in the study, however, the sample sizes of these analyzes will be clarified during writing.

Oversight mechanism

An independent results and dropout rate monitoring committee will not be necessary. However, monitoring will be carried out by the project team.

Safety monitoring: Every month, from the time when 10 patients have been recruited, safety data (dropout, major side effects (requiring discontinuation of treatment) and persistence of neurological symptoms (yes or no)) will be compared in both groups. If a difference of more than 50% is identified for any of these data, the ethics committee will immediately **be** informed. A modification or discontinuation of the study will then be evaluated for reasons of safety, theoretical efficacy or futility.

Limitations of the study

Obviously, our study includes several sources of bias that we anticipate, however we will try to limit their impacts.

Selection bias

The patients who will be selected in our study may not represent the target population of our study. Indeed, a bias of voluntarism is inherent in the estimate of our study. Patients agreeing to participate in a study often do not have the same characteristics as those refusing, causing a gap between the study population and the target population. To limit the impact of this bias, we have designed our study so that it does not represent additional displacement or test for patients, in order to limit refusals to participate. In addition, the use of a non-probability sample can lead to a reference bias. Patients attending the coordinating center may differ from those attending another, for environmental, geographic or other reasons. To limit this bias, by using a multicenter study, we took several centers that are geographically distant, which will represent the general population more fairly. In addition, the recruitment being done in a similar way for the two groups and the matching according to the home hospitals will allow to balance these possible differences which could interfere during the recruitment.

Measurement bias

Some fluctuation in the measuring instrument (questionnaire) may occur. In fact, over time, the patient may find the questionnaire redundant and become bored, and therefore respond less well to it. To limit the impact of this factor, we have limited the number of follow-ups. In addition, in order to balance this fluctuation in the two groups, we will use the same questionnaires in both groups.

Compliance bias

Because TPM causes more side effects than LEV, compliance in this group may be lower. To limit the impact of this bias, active monitoring will be carried out with patients in the event of significant side effects, in order to reduce the dose of their treatment. This will limit drop-outs, as well as encourage better compliance. Then, the antiepileptics will be introduced gradually, in order to limit the side effects which would lead to a decrease in compliance.

Desirability bias

Because patients will know with which antiepileptic drug they will be assigned to, they could involuntarily change their different responses during assessments. Indeed, they might be tempted to demonstrate that TPM, treatment intervention, is more effective than it actually is. The same goes for side effects, which might be exaggerated by a patient knowing to take TPM, which is known to cause more side effects. To limit this bias, with the agreement of the ethics committee, we will approach patients during consent in a non-nominal manner. Indeed, while explaining that the two treatments are as effective as each other in epilepsy, we will explain that we want to demonstrate whether there is superiority of one of the two drugs over the other. Our hypothesis considering TPM being more efficient would remain confidential especially as this remains hypothetical. In the same sense, upon consent, all possible side effects will be presented in the form of a list, not distinguishing which are found more with which antiepileptic. Thus, even knowing the antiepileptic medication prescribed, patients will not be able to influence their responses for or against a particular treatment, not knowing which characteristics belong to which treatment. The two groups will therefore have the same potential information regarding their antiepileptic drug.

Other limitations :

The effect of Leveracetam on cortical depolarizations remains conflicting, however, if present, it may lessen the impact of our results. In addition, the favorable natural course of cortical depolarizations could mask the significant difference between our two groups.

Time and personnel management

Initial and follow-up in-clinic assessments will be performed during regular hospital hours. Telephone assessments will be carried out during the day or evening by a member of the research team.

Ethics

Consent

Before signing the consent form, patients will be informed about the subject and purpose of the study. There will also be an explanation of the antiepileptics used. A list of common and serious side effects of the two treatments will be provided and explained. This list will not indicate which side effect is attributed to which antiepileptic drug, in order to limit the desirability bias (see desirability bias above). The consent must meet the same criteria as usual; the patient must be able to offer free and informed consent. Substituted consent in the event of incapacity, with the most significant relative, at the bedside or by phone will also be authorized. Patients will be clearly informed, verbally and in writing, that participation in the study is voluntary and that they can withdraw at any time during the study. We will also explain that termination of participation in the study will not limit the treatment of their condition and medical monitoring will be provided.

Confidentiality

The confidentiality of personal information and patient results will be ensured throughout the study. Indeed, during the randomization, a random number will be provided to each patient. A file indicating these identification numbers associated with the names of the patients and their contact information will be designed separately from the data collection file. These two documents will be kept separately in the research nurse's office. They will stay at the CHUS at all times.

By agreeing to participate in the study, patients agree that research staff have access to their medical records during recruitment and then subsequently as needed. Eventually, the results of the study will be published in a medical journal, ensuring patient confidentiality.

Risks of participating in the study

The two drugs used in the study carry certain risks and side effects. Levetiracetam can cause depression or psychosis. These effects may rarely be severe but are reversible. In addition, it is important to understand that this drug would likely be the one proposed without this study, being the best tolerated and easiest to use of all antiepileptics. This risk would therefore be the same, with or without the study. As for Topiramate, it mainly

causes gastrointestinal side effects. These are relatively frequent, but reversible and mainly lead to stopping the drug. Its use is therefore less in usual clinic, because compliance is more difficult to obtain. Thus, by participating in the study, some patients may experience these side effects and have to stop this medication, causing some loss in follow-up. They can stop the medicine without prejudice at any time during the study.

Finally, the insertion of an ECoG electrode is associated with a minimal, but higher risk of postoperative infection (1%). Continuous monitoring for a maximum of 72 hours will also require the patient to remain connected to the devices in their room during this period. ECoG is not expected to increase the length of hospital stay, as the protocol is designed to respect the usual recovery of patients following cSDH drainage.

Anticipated impact

We believe that the results of this project, negative or not, will be of great importance. Indeed, this study being the first on the subject and the pathology in question being frequent, our intervention could offer a new treatment for patients with cSDH and TNS not responding to the usual treatments but could also interest other researchers. TNS have a major impact on lives of patients. For example, as long as there is a suspicion of epilepsy, a patient loses his driver's license for 6 months after each neurological episode. This can have a significant impact on the life of a patient, but also for society. So, now that we know from our preliminary study that there is possibly an effective treatment for this condition, it is our duty to test this hypothesis.

Dissemination of results

We plan to publish our results in a scientific journal, whether negative or positive. We would also like to present them at neurology and neurosurgery congresses. The target audience therefore represents people working in research, neurology and neurosurgery.

Date Intervention	
04/2020	Submission of the protocol to the ethics
	and research committee
08/2020	Final approval of the research protocol
09/2020	Final agreements on the participation of
	other participating centers
10/2020	Hiring of the research nurse
10/2020	Start of randomization
10/2022	End of randomization
12/2022	End of writing and submission

Timeline

Budget

- There will be no cost for antiepileptics, which will be prescribed and obtained from the patients' respective community pharmacies.

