probably around 30-40%, a sample of a total of 42 patients with NESIS seems justified. Then, considering that nearly a third of patients will have a NESIS score of less than 4 (non NESIS), 56 patients should be included in the study. Finally, given the number of refusals to participate in the study, probably nearly half of the patients, we plan to approach at least 120 patients.

The final recruitment target is therefore 56 patients (Figure 2).

Figure 2 – Patients distribution

Sample disponibility

The number of participants to be randomized is acceptable and feasible but will require a multi-center design. In fact, during the retrospective study at the CHUS from March 2016 to March 2018²⁸, 18 patients with TNS in the context of cSDH with negative EEGs were identified. Thus, considering at least 4 centers participating in the study, the inclusion of 56 patients in 3 years seems realistic. Moreover, the NESIS entity being newly recognized (mentioned only since 2018), the incidence of NESIS is probably higher than what was found between 2016-2018, the patients being now more easily identified and classified.

Patient recruitment

Patients will initially be identified by neurosurgeons and neurologists from participating centers. These physicians will be aware of the existence of our study and will have the list of inclusion and exclusion criteria. They will therefore be able to inform us when a potential candidate is hospitalized.

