The intervention (Topiramate versus Levetiracetam) will be initiated in the hospital and then, initially, a prescription will be given to the patient for the community pharmacy.

Topiramate will be initiated at 50 mg BID, with an expected increase of 50 mg per week until symptoms are controlled or up to a maximum titration of 100 mg BID.

Levetiracetam will be initiated at 500 mg BID, with an expected increase of 1000 mg divided into 2 doses per week until symptoms are controlled or up to a maximum titration of 1500 mg BID.

The drugs could be reduced or stopped after discussion with a doctor because of side effects or no improvement in TNS.

Follow-up

There will be two phone follow-ups (2nd week and 6th month), as well as two clinical follow-ups (2nd and 4th month).

Phone follow-up: Medical evaluation by a resident, neurologist or neurosurgeon participating in the study. The person administering the assessment will follow a standardized questionnaire so as not to omit information relevant to the study. This assessment includes characterization of transient neurological symptoms and investigation of side effects.

Clinical follow-up: The patient will bring his study notebook to the appointment, in which he will have recorded the various TNS or side effects that have occurred in recent weeks. The appointment will be made by a neurologist or a neurosurgeon (all patients will have a meeting with each of the two specialists). The doctor will therefore carry out an evaluation of TNS and side effects, by completing the standardized questionnaire, which will help to limit the missing data.

The last follow-up will take place at 6 months, a date that we have based on the various studies in cortical depression which have demonstrated maximum effectiveness of TPM at 17 weeks²³. As we did experience in our community, we believe that a significant difference could emerge even earlier.

Losses during follow-up: patients who do not come to the follow-up appointment will be contacted again. In the event of a refusal to attend follow-up or a second absence from an appointment, with the patient's consent, a medical assessment may be completed by phone.

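### The Timeline gives 24 months of randomisation and submission in 12/2022, against 3 years of inclusion and a 6-month last follow-up elsewhere; secondarily, 56 does not follow from the stated NESIS share

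*Protocol*

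**What the plan says.** **Recruitment period.** The section on sample availability (headed Sample disponibility) reports that at the coordinating centre, from March 2016 to March 2018, "18 patients with TNS in the context of cSDH with negative EEGs were identified". From this it concludes that "considering at least 4 centers participating in the study, the inclusion of 56 patients in 3 years seems realistic", adding that "the incidence of NESIS is probably higher than what was found between 2016-2018". The Timeline table dates "Start of randomization" at 10/2020, "End of randomization" at 10/2022 and "End of writing and submission" at 12/2022.

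**Follow-up.** The Follow-up section states: "The last follow-up will take place at 6 months". The participant calendar (Table 4) also ends with a month-6 telephone contact.

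**Total.** The Sample size section aims at about 30 analysed NESIS patients (15 per arm). It raises this to 42 for a loss of 30 to 40%, and then to 56 because a little under one third of patients are expected to be non-NESIS. The same section gives the split as 72% NESIS and 28% non-NESIS. It plans to approach at least 120 patients, "given the number of refusals to participate in the study, probably nearly half of the patients".

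**The concern.** The feasibility argument and the Timeline describe two different recruitment periods, 36 months and 24 months, with no explanation of the difference. The Timeline also leaves two months between the last randomisation and submission, while each patient is followed for six. Read literally, the report would be submitted before the last-recruited patients reach their final assessment. An ethics committee, a funder or a participating centre cannot tell which timetable applies.

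The step from 42 NESIS patients to 56 in total also uses a share that the readable text does not state, so the NESIS numbers to be expected from 56 are slightly overstated. The NESIS comparison is the one the trial is sized for, so that yield should be given correctly even though the discrepancy is small.

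**Working it through.** **1. Dates alone (no accrual assumption)**

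- Randomisation in the Timeline: 10/2020 to 10/2022 = 24 months. Sample disponibility: 3 years = 36 months.
- Last patient: 10/2022 + 6 months = 04/2023, four months after 12/2022.
- Latest randomisation that reaches month 6 by 12/2022: 12/2022 − 6 months = 06/2022, which is month 20 of 24.
- Share randomised later, if accrual is even: 4/24 = one sixth. For 56 patients that is 56 × 4/24 = 9.3.

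**2. Which period fits the protocol's own inputs (illustration only)**

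Inputs: 18 eligible-type patients in 24 months at the coordinating centre and about half refusing, both from the protocol. Assumptions: exactly 4 centres, each matching the coordinating centre, and nobody removed by the exclusion criteria.

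- Approached per month: 18/24 × 4 = 3.0. Enrolled per month: 3.0 × 0.5 = 1.5.
- 36 months: 108 approached, 54 enrolled. This comes close to the protocol's 120 and 56.
- 24 months: 72 approached, 36 enrolled.
- Time to 56 at this rate: 56/1.5 = 37.3, so about 38 months.
- To reach 56 in 24 months: 56/36 = 1.56 times this rate at 4 centres. Alternatively, with 18 × 0.5 = 9 enrolled per centre in 24 months, 56/9 = 6.2, so 7 centres.

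**3. From 42 NESIS patients to 56 in total**

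- Reproducing the stated figure: 42 × 4/3 = 56, so 42/56 = 75% NESIS.
- At the stated 72%: 42/0.72 = 58.3, so 59 enrolled.
- Yield of 56 at 72%: 56 × 0.72 = 40.3 NESIS patients.
- Evaluable, if every loss lacks the primary outcome: 40.3 × 0.70 = 28.2 at 30% loss and 40.3 × 0.60 = 24.2 at 40% loss, or about 12 to 14 per arm.
- Bound, if the non-NESIS share were a full third: 42/(2/3) = 63 enrolled. 56 × 2/3 = 37.3 NESIS patients, of whom 26.1 (30% loss) to 22.4 (40% loss) are evaluable.

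**4. Effect on power**

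Exact power of the uncorrected two-sided chi-square test at 5%, for 14% versus 100%, is 99.1% at 7 per arm and above 99.9% at 11 per arm. At 12 to 14 per arm the planned comparison loses nothing that matters.

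**The case against.** The strongest reply is that enrolment is defined by number, not by date. The target is 56, and no section says that randomisation stops in 10/2022 whatever the count. The Timeline is a planning table, and slow accrual would move its dates. The reply stands, and it limits the consequence.

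A reader might infer that the trial would close with about 36 patients and only 7 to 9 evaluable NESIS patients per arm. The documents do not support this. They contain no such closing rule, and the 36 is a projection that can err in either direction. The protocol speaks of a minimum of 4 centres and expects incidence to have risen, both of which would raise it. The exclusion criteria and centres smaller than the coordinating one would lower it.

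The reply does not remove the date conflict. More centres or a higher incidence could make 24 months feasible, but the protocol quantifies neither, and neither affects the gap between 12/2022 and the last month-6 contact. An earlier endpoint would not close that gap either: the month-4 visit falls after 12/2022 for anyone randomised after about 08/2022.

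On the total, it is fair to say that 28% is itself a little under one third, so the two descriptions of the split are compatible. The full-third figures are therefore bounds, not a second estimate. At 72% and 30% loss, 28.2 evaluable can pass for nearly 30 in a calculation worded throughout as approximate. Figure 2 is also not visible in the text at hand. What stands is that 56 implies 75%, a share that the readable text never gives.

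**Conclusion.** The point holds as an inconsistency in the planning figures. The two recruitment periods differ by 12 months, and the stated submission date precedes the final follow-up of the last-randomised patient by four months. Under even 24-month accrual, about one sixth of patients would be affected. This part rests only on printed dates and the 6-month follow-up.

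That 3 years is the better-supported period is an indication, resting on the four-centre, equal-rate and half-refusal assumptions above.

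The total of 56 is a secondary and small matter. At the stated 72%, it yields about 40 NESIS patients, not 42, and about 24 to 28 evaluable at the stated loss rates. A reader might infer that the trial is therefore underpowered. At the planned 14% versus 100% it is not. What needs correcting is the stated timetable and yield, not the size of the trial.

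**What to change.** - **Recruitment period.** Reconcile the Timeline with the 3 years in Sample disponibility, or state the number of centres or the accrual rate that makes 24 months achievable.
- **Submission date.** Place analysis and submission after the last randomised patient's month-6 contact. That is not before 04/2023 if randomisation ends in 10/2022, 04/2024 if it runs 36 months from 10/2020, and about 06/2024 if it runs 38 months.
- **Yield.** Keep 56 and restate what it is expected to give: about 40 NESIS patients enrolled and about 24 to 28 evaluable (12 to 14 per arm), naming the 72% share and the 30 to 40% loss used.

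The cost is a few edited lines and no extra patients. Adopting the 3-year period lengthens the Timeline's recruitment window by 12 months, or by about 14 at the illustrative four-centre rate. Keeping 24 months would need about 3 more centres at that rate, or a justified higher accrual rate.
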